#### **Brief Summary:**

The study's aim is to enhance current immunization activities in community pharmacies through targeting the two most commonly available non-seasonal vaccines in community pharmacies, namely pneumococcal and herpes zoster vaccination services. The study will compare the change in the number of pneumococcal and herpes zoster vaccinations administered in pharmacy from the corresponding 6-month period prior to the intervention to the 6-month intervention period between intervention pharmacies and the control pharmacies.

#### **Detailed Description:**

Community pharmacies are in a unique position and have potential to help increase immunization rates, especially among those who do not visit their primary care provider regularly. This study seeks to increase the level of pharmacy-based immunization delivery.

The study intervention is designed to increase the current level of pharmacy-based immunization delivery and foster practice change to sustain the intervention effect. Our intervention combines evidence-based strategies for improving immunization coverage and strategies to overcome system barriers to increase sustainability of the intervention over time. The study will focus on pneumococcal and herpes zoster vaccination services.

#### **Specific aims include:**

1. To compare the change in the number of pneumococcal and herpes zoster vaccinations administered in pharmacy from the corresponding 6-month period prior to the intervention to the 6-month intervention period between intervention pharmacies and the control pharmacies. The pre-intervention period will correspond to the intervention period.
2. To compare the extent of immunization activity implementation during the intervention period between intervention pharmacies and control pharmacies.
3. To compare the level of sustainability of immunization services over the period of 6 months after the intervention period ends between the intervention group and the control group.
4. To explore facilitators and barriers to implementing immunization services.
5. To explore factors affecting patient acceptance of pharmacist's vaccine recommendations within the intervention pharmacies.

[figure not shown]
#### **Research Methods:**

This study utilized a two-group randomized controlled trial (RCT) design in community pharmacies in Alabama and California beginning in May 2016 to assess the effect of the training program. One group received an enhanced training program and immunization update while the other group (control) only received immunization update. The primary outcome was the change in pneumococcal and herpes zoster vaccine doses during the 6-month intervention period from the baseline period. The unit of analysis was at the pharmacy level.

Community pharmacies in five counties in Alabama (Montgomery, Jefferson, Mobile, Tuscaloosa, Lee) and four counties in California (San Bernadino, Riverside, Los Angeles, San Diego) were identified using Hayes Directory. Given the higher proportion of African Americans and Hispanics in Alabama and California compared to the national average, these states were chosen in order to ensure that pharmacies serving a minority population would be reached. Comparable counties in each state were selected in terms of proportion of adults over age 65 and annual income (after adjusting for cost-of-living). Pharmacies were recruited to participate in the study via telephone with a maximum of five contact attempts, beginning with the first county in each state (Montgomery and San Bernadino) and exhausting the list of pharmacies before moving on to the next county. Pharmacies were eligible to participate if they: 1) provided direct (walk-in) prescription dispensing services; and 2) offered pneumococcal or herpes zoster vaccinations for the previous twelve months. Pharmacies being considered for sale, closure, or relocation in the next twelve months were excluded from participation. A team-oriented approach was used with each enrolled pharmacy contributing one pharmacist-technician pair, with the pharmacist serving as an immunization champion for the site.

Based on a power calculation (effect size= 19.6 doses, SD=35.5, alpha=0.05) [2], it was determined that a minimum sample size of 64 (32 per group) was needed to assess change in number of vaccine doses between groups pre and-post intervention with 80% power.

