## Data analysis

For the primary outcome (self-reported number of pneumococcal and herpes zoster vaccine doses administered), median change in number of doses from pre- to post-intervention were compared between groups using one-tailed Mann-Whitney U tests.

For the secondary outcome, number of process activities engaged by participants in the two groups were compared using one-tailed Wilcoxon Signed-Rank tests for paired data.

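### The stated 32 pharmacies per group does not follow from the stated inputs; with 35.5 as the SD of change and roughly normal data, the planned one-tailed comparison needs about 42 to 44 per group

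*Combined protocol and SAP*

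**What the plan says.** Research Methods in the combined protocol and SAP defines the outcome: "The primary outcome was the change in pneumococcal and herpes zoster vaccine doses during the 6-month intervention period from the baseline period". It fixes the level of analysis: "The unit of analysis was at the pharmacy level". The sample-size sentence in the same section lists "effect size= 19.6 doses, SD=35.5, alpha=0.05", cites a source, and concludes that "a minimum sample size of 64 (32 per group) was needed to assess change in number of vaccine doses between groups", at 80% power.

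That sentence names neither the test nor the number of sides. It does not say whether 35.5 is the SD of the change or of a single six-month count. It mentions no pre-post correlation, covariate adjustment, dropout allowance or distributional shape.

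The test appears only in Data analysis, where change in doses is to be "compared between groups using one-tailed Mann-Whitney U tests".

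**The concern.** The sentence reads as a complete power calculation: a difference, an SD, an alpha, a power and a result. The only SD stands beside an effect on change, so the natural reading is that it is the SD of change. On that reading a two-group calculation gives a number well above 32, by more than rounding or the choice between a t-test and a rank test can explain.

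This is the plan's only sample-size justification, and it supports the primary comparison. A reader weighing a null result will take 80% as the chance that a 19.6-dose effect would have been found. If the true figure is nearer 70%, a null result says less than the plan implies.

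**Working it through.** **Inputs.** Difference 19.6 doses, SD 35.5, alpha 0.05, power 80%, 32 per group with equal allocation (all Research Methods). One-tailed Mann-Whitney test (Data analysis). The pharmacy is the unit of analysis, so no cluster inflation applies. Assumptions for the main calculation: 35.5 is the SD of change, it is equal in both groups, and changes are roughly normal.

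**1. Trying to reproduce 32.** Standardised difference: 19.6/35.5 = 0.552.

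Normal approximation, n per group = 2 × (z_α + z_β)² × (SD/difference)²:

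- One-tailed: 2 × (1.645 + 0.842)² × (35.5/19.6)² = 40.6, so 41.
- Two-tailed: 2 × (1.960 + 0.842)² × (35.5/19.6)² = 51.5, so 52.

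| Method, 80% power | One-tailed 0.05 | Two-tailed 0.05 |
|---|---|---|
| Normal approximation | 41 | 52 |
| t-test (noncentral t) | 42 | 53 |
| Mann-Whitney, normal data (efficiency 3/π = 0.955) | 44 | 55 |

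The one-tailed Mann-Whitney entry is the unrounded t-test size over the efficiency: 41.3/0.955 = 43.2, so 44. Simulation of the one-tailed Mann-Whitney test with normal data (40,000 runs) gave 79.4% power at 43 per group and 80.5% at 44. No entry is near 32.

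**2. Power at 32 per group.** The noncentrality is 0.552 × √(32/2) = 2.21. One-tailed power is 70.5% by noncentral t. The simulated one-tailed Mann-Whitney test with normal data gives 68.1% (20,000 runs).

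**3. Difference detectable with 80% power at 32 per group.** By t-test, 22.3 doses. By simulated Mann-Whitney, power is 79.6% at 22.9 doses and 80.7% at 23.2, so about 23.

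**4. What would give 32.**

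- *A smaller SD of change.* By one-tailed t-test, 19.6/(22.31/35.5) = 31.2.
- *35.5 as a single-period SD.* Then SD of change = 35.5 × √(2(1 − r)). Setting this to 31.2 gives r = 1 − (31.2/35.5)²/2 = 0.61. One-tailed t-test power at 32 per group, by correlation:

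| r | 0 | 0.25 | 0.5 | 0.61 | 0.7 |
|---|---|---|---|---|---|
| Power | 46% | 56% | 70.5% | 80% | 88% |

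- *Baseline adjustment.* With 35.5 as a single-period SD and r of about 0.46 one-tailed (0.62 two-tailed), an ANCOVA formula gives 32. The plan describes no such adjustment.
- *A looser alpha.* One-tailed 0.10 gives 30 by the normal approximation, but the plan states 0.05.
- *A one-group paired formula.* This gives 22 one-tailed or 28 two-tailed by t-test. Inflating 28 for an assumed 10% dropout gives 28/0.9 = 31.1, so 32. That sizes a within-group change, not the between-group comparison named, and the plan states no dropout rate.

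**5. Effect of data shape.** With SD of change 35.5, a pure location shift and 32 per group, simulated one-tailed Mann-Whitney power is:

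| Shape | Power |
|---|---|
| Uniform | 65% |
| Normal | 68% |
| Logistic | 73% |
| t (4 df), Laplace, gamma (shape 2) | about 82% |
| Exponential | 91% |

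The documents give no shape, so these are assumptions.

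**The case against.** The strongest reply is that 32 may be sound and only under-reported. The SD comes from a cited source and could describe a single period; a correlation of 0.61 then recovers 32, and 0.7 gives 88% power. Vaccine counts may also be skewed or heavy-tailed, and step 5 shows that some such shapes take the Mann-Whitney test past 80% at 32 per group even with an SD of change of 35.5. So 42 to 44 is not a general requirement. It depends on both the meaning of the SD and the shape of the data.

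That stands as a limit on the claim, but it does not rescue the sentence. Each route to 32 needs an input that is not in the plan, and a mean difference, an SD and an alpha carry no information about correlation or shape. The shape argument also works only for fairly skewed or heavy-tailed data under a pure shift; logistic data still leave power at 73%.

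It is also fair that the text is in the past tense, that 64 is called a minimum, and that the enrolled number is not given. Recalculation cannot change recruitment, and achieved power may differ from the figures here. A confidence interval for the observed difference would tell a reader more about a null result than any power figure. None of this removes the need for the plan's own power statement to be correct.

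**Conclusion.** The concern holds. No standard two-group calculation at alpha 0.05, one- or two-tailed, gives 32 per group from the listed inputs. If 35.5 is the SD of change and data are roughly normal, the planned one-tailed comparison needs 84 pharmacies by t-test or about 88 by Mann-Whitney, against the stated 64. That is a shortfall of 10 to 12 per group.

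Confidence is high that the figure cannot be reproduced as reported. Whether 32 was in fact too few cannot be settled from the documents: a stated correlation, a smaller SD of change or a suitable non-normal shape could support it.

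**What to change.** Say first what 35.5 is the SD of, and which test, number of sides and any correlation or other assumption produced 32. If there was such an input, add it and recompute for the planned test. If there was none, replace the power sentence with wording such as:

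> With 32 pharmacies per group, an SD of change of 35.5 and one-tailed alpha 0.05, the Mann-Whitney test has about 68% power to detect a 19.6-dose difference in change, assuming normal data (70% by t-test); the difference detectable with 80% power is about 23 doses (22.3 by t-test).

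The cost is one sentence. It needs no additional pharmacies and no change to the design or the test. The only downside is a less favourable stated power, unless the missing input is supplied and supports 80%.

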## Study Procedures

12

## Data analysis

For the primary outcome (self-reported number of pneumococcal and herpes zoster vaccine doses administered), median change in number of doses from pre- to post-intervention were compared between groups using one-tailed Mann-Whitney U tests.

For the secondary outcome, number of process activities engaged by participants in the two groups were compared using one-tailed Wilcoxon Signed-Rank tests for paired data.

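### The primary and secondary tests are one-tailed without a stated reason, and the sidedness of alpha=0.05 is not given; if 0.05 is applied one-tailed, the false-benefit error is 5% rather than 2.5%

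*Combined protocol and SAP*

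**What the plan says.** The Data analysis section of the combined protocol and SAP specifies that, for the primary outcome, "median change in number of doses from pre- to post-intervention were compared between groups using one-tailed Mann-Whitney U tests". For the secondary outcome, the numbers of process activities in the two groups are to be "compared using one-tailed Wilcoxon Signed-Rank tests for paired data". Neither sentence gives a reason for testing in one direction, and neither repeats a significance level.

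The one level in the document is in the power calculation under Research Methods: "effect size= 19.6 doses, SD=35.5, alpha=0.05". It is not said to be one- or two-sided. From these inputs the plan concludes that "a minimum sample size of 64 (32 per group) was needed to assess change in number of vaccine doses between groups", with 80% power.

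On direction, the document points two ways. The first three Specific aims set out to compare the groups and name no expected direction, and the Brief Summary does the same. The Detailed Description, however, gives raising immunization delivery as the goal. The arms differ by an add-on: "One group received an enhanced training program and immunization update while the other group (control) only received immunization update".

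**The concern.** A one-tailed test needs two things on record: why a result in the other direction would not matter, and the level at which the single tail is tested. The plan gives neither. A hoped-for direction does not by itself make a worse result impossible or irrelevant, and the neutral wording of the aims suggests that either direction would be an answer.

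The success criterion for the primary outcome is what is at stake. With 0.05 in one tail, a weaker advantage for the enhanced training counts as success than under a two-sided 5% test, and a worse result could not be declared by the test at all. With 0.025 in one tail, the standard for claiming benefit is the same as that of the two-sided test. A reader cannot tell which of these applies.

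**Working it through.** **Inputs.** One-tailed tests, from Data analysis. Difference δ = 19.6 doses, SD = 35.5, alpha = 0.05, 80% power and 32 per group, from Research Methods. Assumptions that the document does not state: 0.05 is the level of the planned tests, and 35.5 is the SD of the change.

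**1. Can the sample size reveal the intended sidedness?** The standard formula is n per group = 2(z_α + z_β)²(SD/δ)², with (35.5/19.6)² = 3.281.
- One-sided 0.05: 2 × (1.645 + 0.842)² × 3.281 = 40.6, so 41 per group (82 in total).
- Two-sided 0.05: 2 × (1.960 + 0.842)² × 3.281 = 51.5, so 52 per group (104 in total).

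The plan's 32 per group is reproduced by neither, so it does not show which sidedness was meant.

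**2. False-benefit error.** Under no difference, a one-tailed test at 0.05 claims benefit with probability 0.05. A two-sided test at 0.05 does so with probability 0.05/2 = 0.025. The ratio is 2, whatever the sample size. Total error is 0.05 in both cases; the two-sided test divides it between the directions. One-tailed 0.025 gives no doubling.

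**3. Which results change verdict.** Those in the favourable direction with a one-tailed p between about 0.025 and 0.05. As an illustration only, take exactly 32 per group and no ties, so that there are 32 × 32 = 1024 between-group pairs. The exact Mann-Whitney null distribution gives:

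| Rule | Smallest U for success | Exact tail | Tail at U one lower | Share of pairs |
|---|---|---|---|---|
| One-tailed 0.05 | 636 | 0.0487 | 0.0501 | 636/1024 = 62.1% |
| Two-sided 0.05 | 659 | 0.0243 | 0.0251 | 659/1024 = 64.4% |

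The share is the proportion of pairs in which the intervention pharmacy has the larger change. In this setting U from 636 to 658 succeeds under one rule and fails under the other.

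In doses, by the t approximation, SE = 35.5 × √(2/32) = 8.875. The critical difference is 8.875 × t(62, 0.95) = 14.8 one-tailed and 8.875 × t(62, 0.975) = 17.7 two-sided.

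**4. Power at 32 per group.** The standardised effect is 19.6/35.5 = 0.552.

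| Method | One-tailed 0.05 | Two-sided 0.05 | Gap |
|---|---|---|---|
| t-test | 70.5% | 58.5% | 12.0 points |
| Mann-Whitney, normal data, 100,000 simulated trials | 68.3% | 56.1% | 12.2 points |

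On the plan's own inputs, then, about 12% of trials would be significant under the one-tailed rule only. No entry reaches 80%.

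**The case against.** The strongest reply is that this is largely a matter of convention. The one-tailed choice is declared openly and contradicts no other statement in the plan. There is a respectable argument for it: enhanced training is added to an update that both groups receive, the purpose is to raise delivery, and a null and a negative result might lead to the same decision. Any exact one-tailed p in the favourable direction can be roughly doubled by the reader, and an adverse direction can still be described. Much of this stands. A one-tailed test is not invalid in itself, and what is missing is its justification and its level. But the plan does not make the argument, and its aims are worded otherwise.

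The detailed figures also rest on assumptions. The plan calls 64 a minimum, changes in dose counts are integers and are likely to tie, and a rank test was chosen, so normal data cannot be taken for granted. The plural in the primary-outcome sentence may mean one test per vaccine. This stands against reading the U cut-offs as the trial's actual thresholds. It does not touch the 5% against 2.5% contrast, which applies to each test at its nominal level.

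Two stronger readings are tempting. A reader might infer that the plan gives no significance level at all; it does give 0.05, and what is missing is its sidedness and its link to the planned tests. A reader might also infer that one-tailed testing explains why the stated power is not reached; the shortfall appears under either sidedness and is a separate matter.

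**Conclusion.** The point holds in a limited form. The tests are one-tailed without a reason, beside aims worded without direction, and the only alpha has no stated sidedness. If 0.05 is applied one-tailed, the error in the favourable direction is 5% rather than 2.5%. Results with a one-tailed p between about 0.025 and 0.05 then depend on a choice that the plan does not explain. On the plan's inputs with normal data, that is about one trial in eight.

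A reader might go further and conclude that the total type I error is inflated or that the trial is invalid. The documents do not support that: total error is 5% under either use of 0.05, and the doubling disappears if the level is one-tailed 0.025.

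The stated 80% power is not delivered under either sidedness at 32 per group, if 35.5 is the SD of the change. It therefore needs restating once the sidedness is settled.

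**What to change.** Research Methods and Data analysis are written in the past tense, so the change depends on whether the analysis has been done.

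- **If it is done:** keep the planned one-tailed result. Beside it, report the two-sided Mann-Whitney p-value and the Hodges-Lehmann difference in change with its 95% CI, labelled post hoc.
- **If it is not done:** make the primary test two-sided at 0.05, or one-tailed at 0.025 with the reason stated. Report the same estimate and interval.
- **Secondary outcome:** settle the sidedness in the same way. Whether a paired test suits a comparison of two groups is a separate question.
- **Power statement in Research Methods:** give the sidedness of alpha and say what 35.5 is the SD of. Replace 80% with the figure for the rule used. At 32 per group and on the assumptions above, this is 70.5% one-tailed 0.05 or 58.5% two-sided by t-test, or about 68% or 56% by Mann-Whitney with normal data.

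The extra p-value and interval need no new data. The price of the two-sided rule (or of one-tailed 0.025) is about 12 points of power, which should be stated. No added recruitment is needed.

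### The primary test adjusts for neither state nor, beyond the change score, baseline volume, so it gives up precision that data already in hand could return

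*Combined protocol and SAP*

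**What the plan says.** The Research Methods section describes a "two-group randomized controlled trial (RCT) design in community pharmacies in Alabama and California", analysed at pharmacy level. It defines the endpoint this way: "The primary outcome was the change in pneumococcal and herpes zoster vaccine doses during the 6-month intervention period from the baseline period". The Specific aims section adds that "The pre-intervention period will correspond to the intervention period", so the comparison period is matched for season.

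On how alike the two states are, Research Methods says only this: "Comparable counties in each state were selected in terms of proportion of adults over age 65 and annual income", with income adjusted for cost of living. It does not describe vaccination volume or practice by state.

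The Data analysis section gives the whole primary method in one sentence: "median change in number of doses from pre- to post-intervention were compared between groups using one-tailed Mann-Whitney U tests". No stratum and no covariate is named. The readable text does not say how pharmacies were allocated. The Study Procedures section has no readable content in the text available, so stratified allocation can be neither confirmed nor excluded.

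**The concern.** Baseline doses must be collected to compute the change, and each pharmacy's state is known from recruitment. Neither is used any further. Subtracting baseline is not the same as adjusting for it. Unless pre- and post-intervention counts are almost perfectly correlated, the change score still depends on baseline through regression to the mean, and that dependence stays in the error term. If change also differs by state, that variation stays there too.

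Two things are at stake. The first is precision, which this trial has little of to spare (see the working). The second is chance imbalance. With about 32 pharmacies per arm, one arm may hold more high-volume pharmacies or more pharmacies from one state, and an unadjusted test cannot separate that from the effect of training.

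**Working it through.** **Inputs.** From Research Methods: "effect size= 19.6 doses, SD=35.5, alpha=0.05", 80% power, and "a minimum sample size of 64 (32 per group) was needed to assess change in number of vaccine doses between groups". The document does not say whether 35.5 is the SD of change or of a single-period count; I take it as the SD of change. Not in the documents, and so shown as ranges: the pre-post correlation ρ, the number of pharmacies per state, and any state difference D in mean change.

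**1. The plan's own figure.** n per group = 2(z_α + z_β)² × SD² / δ², with SD²/δ² = 1260.25 / 384.16 = 3.281.
- One-sided: 2 × (1.645 + 0.842)² × 3.281 = 40.6, so 41 per group.
- Two-sided: 2 × (1.960 + 0.842)² × 3.281 = 51.5, so 52 per group.

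The stated 32 is not reproduced. At 32 per group the standard error of the contrast is 35.5 × √(2/32) = 8.875 doses, and 19.6 / 8.875 = 2.208. Power is Φ(2.208 − 1.645) = 71% one-sided and Φ(2.208 − 1.960) = 60% two-sided. The sample size needs reconciling as a separate matter. It bears on this point because it shows how little precision there is to give away.

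**2. Baseline.** With equal SDs σ before and after, the change score has variance 2σ²(1 − ρ), and the baseline-adjusted residual has variance σ²(1 − ρ²). The ratio is (1 + ρ)/2. One-sided power by normal approximation is Φ(19.6 / (8.875 × √ratio) − 1.645).

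| ρ | Variance ratio | Variance cut | Power, normal approximation |
|---|---|---|---|
| change score only | 1.00 | – | 71% |
| 0.5 | 0.75 | 25% | Φ(0.905) = 82% |
| 0.8 | 0.90 | 10% | Φ(0.683) = 75% |
| 0.9 | 0.95 | 5% | Φ(0.621) = 73% |

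The ratio is a result for ordinary analysis of covariance, so I checked it for ranks by simulation (normal data, change SD 35.5, effect 19.6, 32 per group, one-sided 5%). The planned Mann-Whitney test has about 68–69% power. Rank analysis of covariance on baseline has about 77–78% at ρ = 0.5, 74% at 0.65 and 72% at 0.8. At 0.9 the gain is about one point. Type I error was about 5–6%, in line with the planned test.

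**3. State.** Assume 32 pharmacies per state and unstratified allocation. By the hypergeometric distribution, a state splits between arms 18:14 or worse with probability 45%, 19:13 or worse with 21%, and 20:12 or worse with 8%. These probabilities count both directions; halve them for splits in one given direction. The shift in the contrast is (difference in counts / 32) × D.

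| D (doses) | Shift at 19:13 | Shift at 20:12 | Power, pooled test | Power, state-stratified rank test |
|---|---|---|---|---|
| 0 | 0 | 0 | 68% | 67% |
| 10 | 1.9 | 2.5 | 69% | 68% |
| 20 | 3.75 | 5.0 | 68% | 70% |
| 40 | 7.5 | 10.0 | 68% | 82% |

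Power is simulated with the total SD held at 35.5 and 20,000 runs per cell. One-sided type I error averaged over allocations is 4.8% to 5.3% for both tests, and the mean estimated effect is unbiased.

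Given a split of 18:14 or worse, the pooled test's one-sided type I error depends on which arm the split favours. When it favours the intervention arm or the control arm, the error is about 7% or 3% at D = 10, 9% or 2% at D = 20, and 17% or 0.3% at D = 40. These conditional figures carry about one point of simulation noise: at D = 0, where both should be 5%, the runs gave 5.9% and 3.9%.

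**The case against.** The strongest reply is that nothing here is an error. An unadjusted Mann-Whitney test on change is valid under randomisation, its 5% error rate already covers chance imbalance, and adjustment is an efficiency option. That stands, and it sets the size of the point.

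A reader might infer four stronger claims, which the documents do not support:
- **That the two states differ in background vaccination practice.** No passage says so. A difference in trend is an assumption, and a 20-dose difference would exceed the whole target effect.
- **That background trends bias the contrast.** The control is concurrent and randomised, and the baseline is the matching earlier six months, so shared trends cancel in expectation.
- **That baseline volume is ignored.** It is subtracted. What is missing is adjustment for the link between baseline and change that remains.
- **That allocation was unstratified and should be changed.** The section that might say is not readable, and Research Methods is written in the past tense.

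The shifts also need proportion: 3.75 and 5.0 doses are 0.42 and 0.56 of the 8.875-dose standard error. Stratifying by state alone buys almost nothing at D = 20.

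The reply does not dispose of baseline adjustment, which needs no new data and no difference between the states.

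**Conclusion.** The point holds as a loss of precision and an exposure to chance imbalance in the realised trial. It is not a finding of bias or of an invalid test. Almost all of the expected benefit comes from baseline doses: a variance cut of about 25% to 10%, and one-sided power at 32 per group rising from about 68% to about 78% to 72%. This rests on a pre-post correlation of 0.5 to 0.8, equal SDs, normal data and 35.5 being the SD of change. None of these can be confirmed from the documents, and real dose counts may be skewed. With a correlation near 0.9 there is little to gain. State contributes little unless background change differs between the states by much more than 19.6 doses; including it is inexpensive protection against an uneven split.

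**What to change.** Keep the outcome and the population. Make the primary comparison a rank analysis of covariance, for example Quade's: rank the change in doses, adjust it for ranked baseline doses and for state, and compare the adjusted ranks between arms. Keep the unadjusted Mann-Whitney test as a sensitivity analysis. If outcome data have already been examined, reverse the roles: leave the planned test as primary and report the adjusted analysis as a labelled sensitivity analysis.

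State as well whether allocation was stratified by state. If it was, that is a further reason to include state in the analysis.

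The cost is one or two degrees of freedom and slightly more analysis work. No extra pharmacies or data are needed. If the states do not differ, allowing for state costs about one point of power at most (68% to 67% in the simulation).
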